In addition to IM vs standard care, secondary predictors of outcomes following FR will include: demographic factors (age, military rank, race, household income), psychosocial factors (depression, anxiety, anger); sleep quality and fatigue; medical board status for disability; duration of pain-related disability; prescription opioid dosage; and functional capacity measures of strength and endurance. It is expected that service members with more severe psychological distress and disability at baseline will experience lower rates of positive response following FR.

Aim 3. Evaluate the relationship between legacy paper questionnaires included in the PASTOR-plus packet with PASTOR submeasures.

We will compare legacy paper questionnaires completed by study subjects which include the Tampa Kinesiophobia Questionnaire, Patient Activation Measure, Pain Self-Efficacy Questionnaire, Chronic Pain Acceptance Questionnaire and Roland-Morris Disability Questionnaire, and Pain Catastrophizing Scale with PROMIS measures included in the electronic PASTOR assessment, including pain interference, depression, anxiety, anger, and physical function. This will determine if there are legacy questionnaires with prognostic value which should be added to PASTOR.

Aim 4: Evaluate the relationship between self-reported physical function (from PASTOR) and clinician-supervised tests of physical function, such as exercise treadmill test at all time points.

We will compare self-reported physical function with clinician-supervised tests of physical function to determine if PASTOR respondents over or under-estimate their physical capacity.

Aim 5: Determine whether outcomes differ between the subgroup of participants who completed FR program 4 days per week x 3 weeks vs 2 days per week x 6 weeks

During the course of the study, a protocol modification was approved to allow subjects to participate in the FR program with an extended 2 days per week over 6 week schedule with the same number of treatment hours as the original 4 days per week for 3 weeks. We will evaluate outcomes in both groups to determine if one treatment approach yielded superior outcomes to the other.

Aim 6: Compare outcome measures collected within narrow timelines to those collected within flexible timelines.

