We attempted to collect outcome measures at the following timepoints: 1) within one month before starting treatment; 2) within the last day of pre-FR stage through the first day of FR stage; 3) on the last day of FR; 4) 3- and 5) 6- months after the end of FR. However, this precise collection schedule was not always possible. For example, baseline measures were collected more than one month before the start of treatment for study subjects who had conflicts such as military training exercises, personal or family illness or planned leisure travel which postponed the start of study treatment. Collection of follow-up measures was sometimes earlier or later than desired when study subjects with conflicts were unavailable at the time outcomes were requested. We plan to compare outcomes collected within the above timeframes with those collected within timeframes with modest and moderate flexibility as outlined in section 11.3. This analysis will inform the design of future pragmatic clinical trials in determining acceptable timeline parameters for collection of pain outcomes.

Aim 7: Determine if patient activation, pain catastrophizing, self-efficacy or pain acceptance moderates or mediates pain and function outcomes.

We will determine if level of patient activation, catastrophizing, self-efficacy and pain acceptance as measured by legacy questionnaires completed by study subjects have an impact on pain and functional outcomes.

9.5 Study Design:

Describe study design in one to two sentences (e.g., prospective, use of existing records/data /specimens, observational, cross-sectional, interventional, randomized, placebo-controlled, cohort, etc.). Specify the phase – Phase I, II, III, or IV – for FDA-regulated investigational drug research

A comparative effectiveness study, using a prospective randomized cohort design, with patients assigned to either (i) a course of integrative pain management modalities (IM) or (ii) standard care (SC), for three weeks prior to beginning a course of FR.

9.6 Target Population:

Describe the population to whom the study findings will be generalized

Active duty service members with chronic pain

9.7 Benefit to the DoD:

State how this study will impact or be of benefit to the Department of Defense

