During the course of the study, a protocol modification was approved to allow subjects to participate in the FR program with an extended 2 days per week over 6 week schedule with the same number of treatment hours as the original 4 days per week for 3 weeks. We will evaluate outcomes in both groups to determine if one treatment approach yielded superior outcomes to the other.

Analytical Technique: We will use a Sequential Multiple Regression model.⁷⁹ We will assess the relative importance of the FR delivery method (either 4 days per week x 3 weeks vs. 2 days per week x 6 weeks controlling for treatment group on our primary outcomes of pain and physical function as well as on the secondary outcomes measures (depression, anxiety, anger, sleep quality, fatigue, medical board status for disability, duration of pain-related disability, prescription opioid dosage, and functional capacity tests for endurance and strength).

Aim 6: Compare outcome measures collected within narrow timelines to those collected within flexible timelines.

We attempted to collect outcome measures at the following timepoints: 1) within one month before starting treatment; 2) within the last day of pre-FR stage through the first day of FR stage; 3) on the last day of FR; 4) 3- and 5) 6- months after the end of FR. However, this precise collection schedule was not always possible. For example, baseline measures were collected more than one month before the start of treatment for study subjects who had conflicts such as military training exercises, personal or family illness or planned leisure travel which postponed the start of study treatment. Collection of follow-up measures was sometimes earlier or later than desired when study subjects with conflicts were unavailable at the time outcomes were requested. We plan to compare outcomes collected within the above timeframes with those collected within timeframes with modest and moderate flexibility as outlined in the following table. This analysis will inform the design of future pragmatic clinical trials in determining acceptable timeline parameters for collection of pain outcomes.

	Baseline	End of pre-FR stage	End of FR stage	Short-term	Intermediate-term
Narrow timelines	w/in 1 month of treatment start	Last day of pre-FR up to start of FR	Last day of FR	3 months after end of FR	6 months after end of FR

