Modest flexibility	w/in 2 months of treatment start	\leq 2 treatment days before end of pre-FR, through \leq 2 treatment days after start of FR	\leq 2 treatment days before end of FR, through \leq 7 calendar days after end of FR	2-4 months after end of FR	5-7 months after end of FR
Moderate flexibility	w/in 3 months of treatment start thru 2 days after treatment start	\leq 2 treatment days before end of pre-FR, through \leq 4 treatment days after start of FR	\leq 2 treatment days before end of FR, through \leq 30 calendar days after end of FR	1-<5 months after end of FR	6-9 months after end of FR

Analytical Technique: We will use a Sequential Multiple Regression model.⁷⁹ We will assess the relative importance of the timing of assessments on our primary outcomes of pain and physical function as well as on the secondary outcomes measures (pain interference, depression, anxiety, anger, sleep quality, fatigue, medical board status for disability, duration of pain-related disability, prescription opioid dosage, and functional capacity tests for endurance and strength). We will code an indicator variable to document every observation that occurs within the narrow timeline. We will use an interaction term of this indicator with the intervention to see if the intervention shows a differential effect for those who adhere to the narrow assessment timelines.

Aim 7: Determine if patient activation, pain catastrophizing, self-efficacy or pain acceptance moderate or mediates pain and function outcomes.

We will determine if level of patient activation, catastrophizing, self-efficacy and pain acceptance as measured by legacy questionnaires completed by study subjects have an impact on pain and functional outcomes.

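### Aim 6 codes timing only as inside or outside the narrow window, so at 3 months and in the modest 6-month window early and late scores are pooled and a null result cannot show that timing is unimportant

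*Combined protocol and SAP*

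**What the plan says.** Section 9.4 states the objective as "Aim 6: Compare outcome measures collected within narrow timelines to those collected within flexible timelines". Sections 9.4 and 11.3 both explain that the intended schedule could not always be kept. On the visits after treatment, 11.3 says: "Collection of follow-up measures was sometimes earlier or later than desired". On-schedule outcomes are to be compared "with those collected within timeframes with modest and moderate flexibility as outlined in section 11.3", and the stated use is to guide the choice of assessment windows in later pragmatic trials.

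The Aim 6 table in 11.3 sets three tiers per visit. For the short-term visit the narrow entry is "3 months after end of FR", with no tolerance given, and the modest entry is "2-4 months after end of FR"; the moderate entry runs from 1 to just under 5 months.

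The analysis is a sequential multiple regression: "We will assess the relative importance of the timing of assessments on our primary outcomes of pain and physical function". Only one coding of timing follows: "We will code an indicator variable to document every observation that occurs within the narrow timeline". The arm comparison uses the same variable: "We will use an interaction term of this indicator with the intervention". The direction of a departure, its length and its tier are not coded.

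**The concern.** The indicator puts every off-target score in one group. Where the flexible window extends about equally on both sides of the target, that group can mix scores taken too soon with scores taken too late. If pain or function is still moving, these err in opposite directions and the group mean moves back towards the on-target mean. The indicator-by-arm term behaves the same way if the IM effect is growing or fading around the target.

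A null from either term would then have two explanations: timing does not matter, or it matters and the departures offset each other. Aim 6 has to tell these apart, because a later trial may have a different mix of early and late visits. Coding the tiers would not help at 3 months, since the modest and moderate windows there are themselves two-sided.

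**Working it through.** **Where pooling can occur (table in 11.3).**

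| Visit | Modest window | Moderate window | Direction of departures |
|---|---|---|---|
| Baseline | within 2 months before start | within 3 months before, to 2 days after start | essentially early only |
| End of pre-FR | 2 treatment days before, 2 after | 2 before, 4 after | both, a few days |
| End of FR | 2 treatment days before, 7 calendar days after | 2 before, 30 after | mainly late |
| 3 months | 2-4 months | 1-<5 months | both, about ±1 and ±2 months |
| 6 months | 5-7 months | 6-9 months | both in the modest tier; late only in the moderate tier |

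Departures of a month or more on both sides are possible only at 3 months and in the modest 6-month window.

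**Formula.** Let scores change by b SD per month around the target. Among off-target scores let pE and pL be the early and late shares, and mE and mL the mean months early and late. Then:

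- indicator contrast (outside minus inside) = b × (pL × mL − pE × mE)
- indicator-by-arm term = (b in IM − b in SC) × (pL × mL − pE × mE), with the same timing mix in both arms

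Both are zero at any slope when pL × mL = pE × mE.

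**Inputs.** The plan gives no effect size or power for Aim 6. From section 11.2, n = 152, consistent with the enrolment figure: 210 × (1 − 0.28) = 151.2. Everything else is assumed: half the scores on target; the rest uniform from 0.25 month to 1 or 2 months away; residual SD 1; two-sided 5% test; 4,000 simulated data sets per case.

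**Contrast, ±2 months, b = 0.5.** Mean departure = (0.25 + 2)/2 = 1.125 months, so late scores alone shift by 0.5 × 1.125 = 0.56 SD.

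- Even split: 0.5 × (0.5 × 1.125 − 0.5 × 1.125) = 0.
- Three late per early: 0.5 × (0.75 − 0.25) × 1.125 = 0.28 SD, half the late shift.

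**Power, main effect of timing.** The last column is a joint two-degree-of-freedom test.

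| Split, window | b (SD/month) | Indicator | One signed slope | Early and late slopes |
|---|---|---|---|---|
| Even, ±1 month | 0.25 | 5% | 30% | 23% |
| Even, ±1 month | 0.5 | 4-5% | 82% | 73% |
| Even, ±2 months | 0.25 | 4-5% | 75% | 66% |
| Even, ±2 months | 0.5 | 4-5% | >99% | >99% |
| 3 late:1 early, ±2 months | 0.25 | 12-14% | 72-73% | 61-62% |
| 3 late:1 early, ±2 months | 0.5 | 35-36% | >99% | >99% |

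At b = 0.1 every coding stays below 20% (one signed slope 9-19%).

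**Other settings.** These used 3,000 runs, departures uniform from zero, and alpha 0.025, which 11.3 sets for Aims 1 and 2 (none is stated for Aim 6). With b = 0.3:

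- 1-<5 month window, even split: indicator 3%, signed slope 77%.
- 6-9 month window, all late: 67% against 90%.
- Baseline, all early by up to 2 extra months: 35% against 55%.

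In the last two nothing cancels; the indicator only loses power.

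**The case against.** The strongest reply is that the indicator answers the question as worded. Aim 6 compares narrow with flexible collection; if early and late departures balance, the flexible-window mean really is close to the on-target mean, and a near-zero coefficient reports that correctly. This stands, and is why the indicator should stay. It does not reach the aim's further purpose: a balance that happens to hold in this trial does not make the same window safe in a trial whose visits mostly run late.

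The numbers are also open to challenge. The slopes are assumed, and 0.5 SD per month is steep: half an SD is the plan's own fallback for a minimally important difference on PROMIS measures. At shallow slopes no coding works well. Separate slopes have less power than a single slope, and less again for the interaction: with a trend in one arm only and an even split, about 9% and 22% (±1 month) and 19% and 63% (±2 months) at 0.25 and 0.5 SD per month. All of this stands and limits what the added terms can promise.

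A reader might infer that the indicator tends to zero at nearly every visit however strong the timing effect. The table does not support that: baseline and the 6-9 month window are essentially one-sided, and at the end of pre-FR and the end of FR the early side is at most 2 treatment days. A reader might also infer that the Aim 1 comparison at 3 months is compromised. The indicator belongs to Aim 6 and does not enter that analysis.

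**Conclusion.** The concern holds in a limited form. At 3 months, and in the modest 6-month window, the only coded timing variable can miss a real time trend, or a changing IM effect, because it pools early with late. Cancellation is complete only for a linear trend with balanced departures, and partial otherwise. In the balanced case the indicator's power equals its false-positive rate at any slope, while signed coding of the same data reaches the powers tabulated above. Elsewhere the defect is lost power or a small cancellation.

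How far this affects the actual data cannot be known, because the documents report neither a trend nor the share of early, on-target and late assessments. What does follow is that a null indicator or indicator-by-arm term at these visits is not evidence that timing is unimportant. This affects a secondary, methodological aim.

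**What to change.** In section 11.3, Aim 6:

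- Keep the narrow-window indicator and its interaction for the narrow-versus-flexible comparison.
- Add, for each visit, signed days from target: zero inside the narrow window, otherwise days before (negative) or after (positive) its nearest edge. Measuring from the edge handles baseline and end of pre-FR, where the narrow window is an interval rather than a date.
- Add the product of signed days with treatment arm. Allow separate early and late slopes where both sides occur.
- Base the conclusion on acceptable windows on these terms, with confidence intervals, and report the numbers early, on target and late at each visit.

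The cost is a few more coefficients per model and low power for the interaction, which should be acknowledged when a null is reported. The assessment and treatment dates are already needed to code the indicator, so no new data are required.

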11.0 Statistical/Data Analysis Plan

11.1 Statistical Considerations:

List the statistical methods to be used to address the primary and secondary objectives, specific aims, and/or research hypotheses. Explain how missing data and outliers will be handled in the analysis. The analysis plan should be consistent with the study objectives. Include any sub-group analyses (e.g., gender or age group). Specify statistical methods and variables for each analysis. Describe how confounding variables will be controlled in the data analysis

The statistical methods that will be used for each study aim are explained in section 11.3.

Approach to Missing Data.

The amount of missing data will be first quantified where possible, and determined by the amount of missing data that occurs, three indirect tests of the mechanism of missingness will be explored: (1) baseline demographic characteristics of those who ever and never missed data by group allocation will be compared (an indirect test to rule out missing completely at random [MCAR]); (2) the difference between mean utility scores of participants with missing and non-missing data will also be compared (an additional indirect test to rule out MCAR) and (3) controlling for the probability of providing missing data, the mean scores of those that never and ever missed in intervention and control groups will be compared (an indirect test of missing not at random [MNAR]). While analysis using mixed models allows all observed data to be included in the analysis under the assumption that the data are MCAR, if substantial missing data occurs, multiple imputation or mean conditional imputation will be used with subsequent sensitivity analyses to explore the impact of imputation on results. To address the issue of artificially reduced estimates of stochastic uncertainty produced by imputation, bootstrapping procedures will be used on the entire imputation and estimation process.

11.2 Sample Size Estimation:

Estimated required sample size: 152
Estimated participant drop out + withdrawal: 28%
Total enrollment requirement: 210
Total MAMC enrollment: 210

11.3 Data Analysis Plan:

Primary (i.e., primary outcome variables) and secondary endpoints. The primary outcome endpoints are pain intensity and functional status as measured by the PASTOR questionnaire. In addition, secondary predictors of outcomes measures will be evaluated, including demographic factors (age, military rank, household income, race), measures of pain interference, depression, anxiety, anger, sleep quality, fatigue, medical board status for disability, duration of pain-related disability, prescription opioid dosage and functional capacity tests for endurance and strength.

Data analysis.

Aim 1: Evaluate the benefit of a program of multimodal integrative pain management therapies prior to an intensive functional restoration program, relative to standard care.

Hypothesis: Patients who complete an IM program prior to an FR program will demonstrate significantly greater improvements in pain and physical function going into the FR program, relative to standard care. At post-FR, patients who completed an IM program prior to FR will demonstrate significantly improved outcomes on pain severity and physical function at discharge from the program and at 3-months post-FR, relative to standard care.

Analytical Technique: We will use a hierarchical linear model (HLM) for a cluster-randomized trial with time nested within patients.⁷⁷ HLM affords an integrated approach to studying the structure and predictors of individual change, and provides the appropriate standard errors and correct statistical inferences for clustered data. HLM models allow the use of data from patients who are missing one or more observations, where the assumption holds that data are missing at random. Some patients will not follow the intervention protocol, either deliberately by not doing the intervention or due to extenuating circumstances that prevent their participation with the intervention protocol. We will use an intent-to-treat analysis.

We will initially complete analyses without the inclusion of pre-randomization covariate information. In all analyses, the data will be examined for appropriateness of the statistical assumptions underlying fitted models (e.g., distribution of regression residuals, identification of multivariate outliers representing influential data points, tests for departures from linearity). The primary analysis will examine differences between the control and intervention groups' outcome scores at the 3 month assessment point. To control for inflation of Type I error rates due to co-primary outcomes, alpha will be set to 0.025 for each test of the outcome variables.

If recruitment targets are exceeded to a sufficient magnitude, secondary analyses of change in pain severity and physical function using responder analysis will also be performed. When consensus on minimally important difference (MID) exists, that MID will be used to define response. For PROMIS measures that do not have consensus MID measures, an improvement of one-half of one standard deviation on the PROMIS scale will be considered the minimally important difference for a positive response. Responder analyses require higher sample sizes to detect statistically significant differences but are the preferred method of assessing treatment effect, and permit meaningful comparisons between randomized clinical trials.⁷⁸

Aim 2: Identify prognostic factors that predict successful outcomes on pain severity and function following intensive interdisciplinary functional restoration.

In addition to IM vs standard care, secondary predictors of outcomes following FR will include baseline measures of: demographic variables (age, military rank, race, military occupation), pain characteristics (location, duration, character), psychosocial factors (depression, anxiety, anger); sleep quality and fatigue; medical board status for disability; duration of pain-related disability; prescription opioid dosage; and functional capacity tests for endurance and strength.

Analytical Technique: The co-primary outcomes for pain severity and physical function will be analyzed using a Sequential Multiple Regression model.⁷⁹ The model will adjust for baseline measures of the co-primary outcomes and pre-FR treatment groups, before assessing the relative importance of secondary outcomes measures (baseline measures of pain interference, depression, anxiety, anger, sleep quality, fatigue, medical board status for disability, duration of pain-related disability, prescription opioid dosage, and functional capacity tests for endurance and strength). Relative importance of predictors among these secondary outcomes will be reported by their respective regression beta weight coefficients. To control for inflation of Type I error rates due to co-primary outcomes, alpha will be set to 0.025 for each test of the outcome variables in their respective regression models.

Aim 3: Evaluate the relationship between legacy paper questionnaires included in the PASTOR-plus packet with PASTOR submeasures.

We will compare legacy paper questionnaires completed by study subjects which include the Tampa Kinesiophobia Questionnaire, Patient Activation Measure, Pain Self-Efficacy Questionnaire, Chronic Pain Acceptance Questionnaire and Roland-Morris Disability Questionnaire, and Pain Catastrophizing Scale with PROMIS measures included in the electronic PASTOR assessment, including pain interference, depression, anxiety, anger, and physical function. This will determine if there are legacy questionnaires with prognostic value which should be added to PASTOR.

Analytical Technique: We will use correlation analysis to determine the relationship between legacy paper questionnaires and PASTOR submeasures.

Aim 4: Evaluate the relationship between self-reported physical function (from PASTOR) and clinician-supervised tests of physical function, such as exercise treadmill test at all timepoints.

We will compare self-reported physical function with clinician-supervised tests of physical function to determine if PASTOR respondents over or under-estimate their physical capacity.

Analytical Technique: We will use correlation analysis to explore the relationship between self-report and clinician supervised tests of physical function.

Aim 5: Determine whether outcomes differ between the subgroup of participants who completed FR program 4 days per week x 3 weeks vs 2 days per week x 6 weeks.

During the course of the study, a protocol modification was approved to allow subjects to participate in the FR program with an extended 2 days per week over 6 week schedule with the same number of treatment hours as the original 4 days per week for 3 weeks. We will evaluate outcomes in both groups to determine if one treatment approach yielded superior outcomes to the other.

Analytical Technique: We will use a Sequential Multiple Regression model.⁷⁹ We will assess the relative importance of the FR delivery method (either 4 days per week x 3 weeks vs. 2 days per week x 6 weeks controlling for treatment group on our primary outcomes of pain and physical function as well as on the secondary outcomes measures (depression, anxiety, anger, sleep quality, fatigue, medical board status for disability, duration of pain-related disability, prescription opioid dosage, and functional capacity tests for endurance and strength).

Aim 6: Compare outcome measures collected within narrow timelines to those collected within flexible timelines.

We attempted to collect outcome measures at the following timepoints: 1) within one month before starting treatment; 2) within the last day of pre-FR stage through the first day of FR stage; 3) on the last day of FR; 4) 3- and 5) 6- months after the end of FR. However, this precise collection schedule was not always possible. For example, baseline measures were collected more than one month before the start of treatment for study subjects who had conflicts such as military training exercises, personal or family illness or planned leisure travel which postponed the start of study treatment. Collection of follow-up measures was sometimes earlier or later than desired when study subjects with conflicts were unavailable at the time outcomes were requested. We plan to compare outcomes collected within the above timeframes with those collected within timeframes with modest and moderate flexibility as outlined in the following table. This analysis will inform the design of future pragmatic clinical trials in determining acceptable timeline parameters for collection of pain outcomes.

	Baseline	End of pre-FR stage	End of FR stage	Short-term	Intermediate-term
Narrow timelines	w/in 1 month of treatment start	Last day of pre-FR up to start of FR	Last day of FR	3 months after end of FR	6 months after end of FR
Modest flexibility	w/in 2 months of treatment start	\leq 2 treatment days before end of pre-FR, through \leq 2 treatment days after start of FR	\leq 2 treatment days before end of FR, through \leq 7 calendar days after end of FR	2-4 months after end of FR	5-7 months after end of FR
Moderate flexibility	w/in 3 months of treatment start thru 2 days after treatment start	\leq 2 treatment days before end of pre-FR, through \leq 4 treatment days after start of FR	\leq 2 treatment days before end of FR, through \leq 30 calendar days after end of FR	1-<5 months after end of FR	6-9 months after end of FR

Analytical Technique: We will use a Sequential Multiple Regression model.⁷⁹ We will assess the relative importance of the timing of assessments on our primary outcomes of pain and physical function as well as on the secondary outcomes measures (pain interference, depression, anxiety, anger, sleep quality, fatigue, medical board status for disability, duration of pain-related disability, prescription opioid dosage, and functional capacity tests for endurance and strength). We will code an indicator variable to document every observation that occurs within the narrow timeline. We will use an interaction term of this indicator with the intervention to see if the intervention shows a differential effect for those who adhere to the narrow assessment timelines.

Aim 7: Determine if patient activation, pain catastrophizing, self-efficacy or pain acceptance moderate or mediates pain and function outcomes.

We will determine if level of patient activation, catastrophizing, self-efficacy and pain acceptance as measured by legacy questionnaires completed by study subjects have an impact on pain and functional outcomes.

Analytical Technique: We will use a multiple linear regression approach to determine the roles of patient activation, pain catastrophizing, self-efficacy, and pain acceptance with regard to the intervention outcomes. Baron and Kenny⁸⁶ described mediation and moderation testing and their work has been developed further by methodologists. We will use Hayes' conditional process tools⁸⁷ to test if patient activation, pain catastrophizing, self-efficacy, and pain acceptance are affected by the intervention and help explain the outcomes, that is, if they are a mechanism for how the intervention helps people (mediation). We will compare models with and without the mediating variables and partition the total effect of the intervention into indirect effects due to impact on hypothesized mediators and the remaining direct effects. Using interaction terms, we will also examine if these variables may moderate the relationship of the intervention on the outcomes, helping explain who is responding best to the intervention. This approach can be extended to determine if how the intervention works differs by participant characteristics, that is moderated mediation.

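### The third missingness check in section 11.1 is labelled an indirect test of MNAR, but it uses observed scores only and cannot tell MAR from MNAR, whichever way it comes out

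*Combined protocol and SAP*

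**What the plan says.** Under the missing-data approach in section 11.1, the plan states that "three indirect tests of the mechanism of missingness will be explored". In the first, "baseline demographic characteristics of those who ever and never missed data by group allocation will be compared". In the second, "the difference between mean utility scores of participants with missing and non-missing data will also be compared". Both are offered as ways to rule out MCAR. The third adjusts for an estimated probability of missingness and then reads: "the mean scores of those that never and ever missed in intervention and control groups will be compared (an indirect test of missing not"; the parenthesis goes on to name MNAR.

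The section does not say which variables enter the probability model, which score or visit is compared, what significance level applies, or what either result would change. If the amount of missing data is substantial, "multiple imputation or mean conditional imputation will be used with subsequent sensitivity analyses to explore the impact of imputation on results". No analysis that departs from MAR is specified.

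In section 11.3, the Aim 1 hierarchical linear model uses patients with incomplete data "where the assumption holds that data are missing at random". The primary comparison is at 3 months. Section 11.2 expects 28% dropout and withdrawal among 210 enrolled. (Section 11.1 ties the mixed model to MCAR instead; that inconsistency is a separate matter.)

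**The concern.** MNAR means that missingness still depends on the unseen score once the observed data are taken into account. A comparison built from observed scores speaks to a different question: whether missingness is related to observed scores beyond what the probability model explains.

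The third check is the only item in the plan addressed to MNAR, and the Aim 1 model rests on MAR. A significant result could therefore be written up as evidence of MNAR when the model's assumption in fact holds. A non-significant result could be written up as reassurance when it does not. Neither statement would be warranted, and with 28% loss expected a reader of the trial report would give such a statement weight.

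**Working it through.** **1. The plan's own figures.** The plan gives no operating characteristic for this check. The only nearby figure that can be checked is enrolment: 152 / (1 − 0.28) = 211.1, against 210 stated; 210 × 0.72 = 151.2. That agrees to within rounding of the dropout rate, since 1 − 152/210 = 27.6%. If all the expected loss shows up as missed visits, 210 × 0.28 ≈ 59 patients would count as having ever missed.

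**2. Why the label cannot be right.** Let R be the missingness pattern and split the scores into observed and missing parts. Then

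f(y_obs, y_mis, R) = f(y_obs, R) × f(y_mis | y_obs, R).

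The data inform only the first factor. MAR and MNAR differ only in the second: under MAR, f(y_mis | y_obs, R) does not depend on R. The third check is a function of observed scores, R, arm and the fitted probability of missing, so it lies wholly within the first factor. Any MNAR model can be paired with an MAR model that has the same first factor, and the check behaves identically under both. Without further untestable assumptions it cannot discriminate.

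**3. How it behaves in practice.** Simulation inputs from the plan: 210 patients, five assessments (section 10.1) and 28% ever missing (section 11.2). Assumed, not in the documents:
- within-patient correlation 0.3, 0.5 or 0.7;
- log-odds of missing 0.5 or 1.0 per SD;
- intermittent or monotone missingness;
- a second missing rate of 50%;
- an arm effect of 0.3 SD.

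There were 16 settings with 800 or 1,500 trials each. The Monte Carlo standard error is at most √(0.25/800) = 1.8 percentage points.

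The check was coded as a regression of each patient's mean observed post-baseline score (centred by visit and arm) on ever-missed, arm and the fitted logit of ever missing, two-sided 5%. The probability model used arm and demographics (A), or arm, demographics and baseline score (B).

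Share of trials in which the check is significant, range over the 16 settings:

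| Mechanism | A | B |
|---|---|---|
| MCAR | 3–8% | 1–6% |
| MAR on demographics | 3–6% | 0–5% |
| MAR on baseline score | 19–100% | 4–11% |
| MAR on last observed score | 67–100% | 27–100% |
| MNAR on current unseen score | 20–100% | 9–84% |
| MNAR on patient's latent level | 46–100% | 15–98% |
| MNAR on visit-specific deviation only | 2–7% | 1–6% |

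One setting as an example (28% ever missing, monotone, correlation 0.5, log-odds 0.5), shown as A / B: MAR on last observed score 76% / 55%; MNAR on current score 35% / 13%; MNAR on latent level 59% / 24%; MNAR on deviation only 4% / 4%.

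**4. Reading the table.** A significant result arises under MAR whenever the probability model omits the driver. A non-significant result is the usual outcome under MNAR that acts on the unpredictable part of the missed score. Under B, MAR on the last observed score gave more significant results than MNAR on the current score in all 16 settings. The ranges for MAR and MNAR overlap almost entirely, so neither result points to one mechanism.

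**The case against.** The plan calls these checks indirect and exploratory, and the third one is adjusted for the probability of missing data. That adjustment works when the model contains the driver: significance is 0–6% for MAR on demographics, and 4–11% for MAR on baseline score when baseline is modelled. This stands as far as it goes. But the plan lists no variables for the model, and adding baseline still leaves 27–100% under MAR through later observed scores. Calling the check indirect does not supply information that observed scores lack.

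A reader might infer that the check works backwards, passing MNAR and flagging MAR. That is not supported. Missed scores correlate with observed ones, so the check is often significant under MNAR on the current score or latent level (20–100% under A, 9–98% under B).

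A reader might also infer that it rejects too often under MCAR. Rates of 28–31% do appear in simulation if each patient's uncentred mean over all observed visits is used, because early leavers lack the later visits. The plan does not specify that computation, and the centred version above stays at 1–8%.

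Finally, a reader might infer that the 3-month result hinges on this check. Nothing in sections 11.1 to 11.3 says so: imputation is triggered by the amount of missing data, and no threshold or decision rule is attached to the check.

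**Conclusion.** The point holds as a matter of what the check can show. It is non-specific: it can be significant under MAR and non-significant under MNAR, so it neither identifies the mechanism nor supports or undermines the MAR assumption of the Aim 1 model. This follows from the check's use of observed scores alone and needs no simulation. The rejection rates illustrate it, and they depend on the assumed correlation, mechanism and probability-model variables. The consequence is moderate. No planned analysis changes with the result, so the exposure is a wrong statement in the trial report about missingness. It is worth correcting because the correction is cheap and nothing else in the plan addresses departure from MAR.

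**What to change.** In section 11.1:

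- Delete the parenthesis that calls the third check an indirect test of MNAR.
- Relabel it as a descriptive check of whether missingness depends on observed data. Run it visit by visit as a logistic regression of missing the next visit on the last observed pain and function scores, baseline scores, demographics and arm.
- State that its result, significant or not, is not evidence for or against MNAR.

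If departure from MAR is to be addressed, do it through a pre-specified sensitivity analysis of the 3-month co-primary comparison, not through this check. One example is a delta-adjusted version of the multiple imputation that section 11.1 already allows for. That imputation is at present conditional on substantial missing data and is one of two options, so it would have to be fixed in advance for this purpose.

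Cost: one or two sentences, a logistic model on data already held, and slightly more analysis work if the sensitivity analysis is added. The trial loses the ability to report a test of MNAR.
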